### **Randomization Procedures (~1 week)**

If the participant's migraine e-diary and diagnosis confirmation are sufficient for enrollment, the virtual study team will conduct the end of run in call to review information submitted during screening and run-in period. The participant record will then be reviewed by an Investigator and, if eligible, will be randomized; the device shipment will occur thereafter.

When the device kit is received, the participant will need to watch a series of videos on how to set-up and use the Mi-Helper device. Once the training is completed, they will complete a comprehension quiz. The participant will be able to review the study training video at any time within the Study App.

A total of 156 participants will be randomized equally to one of two groups:

- Group I (active treatment): 10 LPM, dehumidified air, 15 minutes total
- Group II (sham [control] treatment): 2 LPM, ambient air administered intermittently via Mi-Helper, 15 minutes total

Upon receipt of the Mi-Helper device, the participant will be instructed to store the shipment at room temperature and to not open the desiccant cartridge and tube set prior to use. The training will also instruct the participants that the device may only be used 'once', during a qualifying migraine attack. A qualifying migraine attack must meet the following criteria based on responses to the Baseline Questionnaire:

- Migraine head pain is at least mild intensity (score of 1=mild, 2=moderate, or 3=severe on the 4-point VRS).
- Onset of migraine head pain was no more than one hour prior to treatment.
- Participant did not wake up with the migraine attack.
- Participant is not experiencing severe sinus congestion.
- Participant did not have migraine related pain in the 48 hours prior to the migraine attack.
- Participant did not take any migraine rescue medications in the 48 hours prior to the migraine attack, such as triptans, NSAIDs, or gepants used for acute treatment.

The participant may reach out to the study team via the Study App, email, or phone to address any questions they have about any study-related procedures.

Participants will have up to 35 days to complete the treatment session after receiving the device.

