### **Baseline Procedures (pre-treatment)**

Baseline assessments will be initiated at the onset of a migraine attack. Baseline assessments will include questions about the participant's head pain, nausea, photosensitivity, phonosensitivity, and the most bothersome symptom (MBS) which will be recorded within the Study App prior to treatment initiation.

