## 7.3 Study Product Handling, Storage, & Accountability

Shipping, Handling and Accountability: After enrollment and randomization, the Mi-Helper device will be shipped to the participant's home address. Device shipping will be organized by the participant through the Study App. Study devices will be shipped to the subject directly. The participant will be required to confirm receipt through the Study App prior to initiating any study-related activities and will be required to record the serial number of the material received. Once the device is received and the participant confirms receipt, they can use the device when they experience a headache that reaches at least mild intensity pain (based on the 4-point VRS scale) as recorded in their eDiary. After the single treatment with the device and completion of all post-treatment assessments, the participant will need to return the device via courier service, which can be organized through the Study App. A log of devices shipped out to participants and received back from the participants will be maintained. See the Investigational Product Management Plan for more details.

If a participant experiences a technical difficulty with the Mi-Helper device that cannot be resolved with real-time troubleshooting, they may be shipped a replacement tubeset and desiccant cartridge to treat their next attack. If this occurs during the last week of their 35 day treatment period, a protocol exception may be granted to extend their treatment period at the discretion of the sponsor and/or investigator.

Storage: The Mi-Helper device, disposable desiccant cartridge, sterile saline bottles and tube set will be stored at room temperature. External packaging for the disposable components will have an additional label stating "do not open before use" to reduce the risk of premature damage or use of study materials. All components should stay in original packaging until the time of treatment.

Refer to the Mi-Helper Quick Start Guide and trial user manual for further details.

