#### **8.1.3 Adverse Event Reporting**

For the purposes of this study the period of observation for AEs begins after baseline procedures and continues through to the participants completion of the study. Any health-related changes prior to the randomization will be recorded as medical history.

All AEs occurring during the study will be individually assessed by the PI, reported and recorded, regardless of seriousness or relationship to the study device. Participants will be able

to report possible AEs for consideration by filling out the ad hoc Change in Health form within the Study App. There will be delegated unblinded Study Team members for the purposes of coordinating shipment logistics in relation to randomization. The participants may also report any changes to their health by chat function in the Study App and may choose to contact the Study Team via phone or email. Once a change in health is reported by the participant, the PI or designee will reach out to the participant in near real-time (within 1 business day) to make health assessments and advise on further steps, including referral to their local doctor for further assessment and treatment, if applicable. The participants will be directed by the Study App or Study Team to go to the nearest emergency room if it's a medical emergency.

The following information will be documented in each case:

- Participant ID
- AE Term
- Start Date of event
- End Date of event or Ongoing
- Severity or Intensity
- Seriousness
- Action taken with study device
- Action taken to treat event
- Outcome
- Relationship to study device
- Expectedness
- Participants health status assessed by PI

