## 9. Participant Completion and Withdrawal

### 9.1 Participant Completion and Withdrawal

Participants will have completed the study once the device is used, all post-treatment procedures are completed at stipulated timepoints, and the study device is returned.

The participant may withdraw from the study at any time by notifying the Study Team. Participants may be withdrawn from the study by the investigator if study procedures have not been followed or if the investigator determines the participant is not able to safely continue with the study due to an AE or other health-related issue.

Participants will have up to 35 days to complete the treatment session after receiving the device, after which they will have to return the device and will be withdrawn from the study.

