6. GENERAL ANALYSIS CONSIDERATIONS

6.1. Analysis Populations

For the purposes of analysis, the following analysis sets are defined:

6.1.1. *Intent-to-Treat (ITT) Population*

- All participants who were randomly assigned to a treatment.

6.1.2. *Modified Intention to Treat (mITT) Population*

- All participants who used the study intervention and completed a baseline and 2-hour post-dose pain assessment.

6.1.3. *Per Protocol (PP) Population*

- All participants in the mITT population that do not have a major protocol deviation related to primary endpoint(s), and completed the primary endpoint(s) and completed the treatment in compliance with the protocol, with group assignment as treated.

The ITT analysis set will serve as the main analysis set for all safety evaluations.

The mITT analysis set will be the primary population used for efficacy analyses in this study.

The primary and secondary efficacy assessments will also be performed on the PP and the ITT analysis sets as a sensitivity analysis.

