7.2. Participant Disposition

Participant disposition will be summarized by study group and overall using Screened, Enrolled, ITT (Randomized/Safety Population), mITT, and PP populations. The number and percentage of participants for each study product will be presented for ITT, mITT, and PP populations. The denominator for percentages will be the number of participants randomized per group.

Discontinued participants will be summarized by product group and overall based on discontinued reasons.

A listing for disposition will include the participants who are randomized and will cover the following information: population assigned (ITT, mITT, and PP), study completion status and reason for discontinuation/screen failure.

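### Safety is analysed on everyone randomised, so participants who never use the device can dilute the reported device-related adverse event incidence

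*SAP*

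**What the plan says.** SAP 6.1 and Protocol 11.3 carry the same sentence: "The ITT analysis set will serve as the main analysis set for all safety evaluations". ITT is everyone randomised; device use is not required. SAP 7.2 confirms the reading by listing the set as "ITT (Randomized/Safety Population"), so the references to a safety population in SAP 7.4, 7.6 and 7.7 do not introduce a separate treated set.

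The sequence of events is also clear:

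- Protocol section 5 (Randomization Procedures): the participant, "if eligible, will be randomized; the device shipment will occur thereafter". Protocol 7.3 agrees: "After enrollment and randomization, the Mi-Helper device will be shipped".
- Protocol section 5 (Baseline Procedures): "Baseline assessments will be initiated at the onset of a migraine attack".
- Protocol 8.1.3: "the period of observation for AEs begins after baseline procedures and continues through to the participants completion of the study".
- Protocol 9.1: participants have 35 days from receipt to treat, "after which they will have to return the device and will be withdrawn from the study".

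The primary safety outcome (Protocol 11.7, SAP 9) is the incidence of device-related AEs in the 48 hours after the session. The arms are compared with Fisher's exact test. SAP 9 also asks for the percentage who did not finish treatment because of discomfort.

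**The concern.** A device-related AE rate is normally read as the risk to someone who uses the device. Here the named denominator can include people who never switched it on. They have no session, no 48-hour window and no AE observation period, so they can add to the denominator but never to the numerator.

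The general rules do not settle how they are handled. SAP 7.1 divides by the number of participants with a non-missing value, and SAP 6.2 rules out imputation. Neither says whether a never-user is missing or is a person with no AE, and SAP 9 gives no denominator of its own. Two programmers could print different incidences from the same data. The tolerability percentage has the same ambiguity.

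The mITT set is not a substitute. It requires device use, but also a 2-hour pain score, so a user who had an AE and skipped that questionnaire would drop out of it.

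Safety is half of the primary objective. What is at stake is the printed absolute incidence and any confidence bound on it, rather than the AE counts or listings.

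**Working it through.** **The plan's own figures.** The documents state no AE rate, so the sample size is the only figure to reproduce (SAP 5, Protocol 11.1). With 41% v 16%, two-sided 5% and Fisher's exact test, full enumeration gives power of 81.7% at 58 per group (80.8% at 57, 79.9% at 56), so the stated 58 is adequate. Then 58 / (1 − 0.25) = 77.3, rounded up to 78 per group, 156 in total. This matches the plan.

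**Inputs for the dilution.**

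- Never-use share q: not given, so ranged. 5% and 10% are illustrative. 20.3% = (172 − 137)/172 = 35/172, from the earlier decentralised study in Protocol 3.2; it applies only if that study's safety population meant treated participants. 25% is the dropout allowance and applies only if all attrition were non-use.
- AE incidence among users r: not given, so ranged from 5% to 30%.

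**Formula.** If non-users count as having no AE, printed incidence = r × (1 − q), and the gap is r × q.

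| Rate among users | q = 5% | q = 10% | q = 20.3% | q = 25% |
|---|---|---|---|---|
| 5% | 4.8% | 4.5% | 4.0% | 3.8% |
| 10% | 9.5% | 9.0% | 8.0% | 7.5% |
| 20% | 19.0% | 18.0% | 15.9% | 15.0% |
| 30% | 28.5% | 27.0% | 23.9% | 22.5% |

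The gap runs from 0.05 × 0.05 = 0.25 points to 0.30 × 0.25 = 7.5 points. If non-users are instead treated as missing, the gap is zero.

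**Confidence bound with no events.** The exact two-sided 95% upper limit is 1 − 0.025^(1/n). At n = 78 it is 4.6%; at n = 58 it is 6.2%. Counting unexposed people overstates how much risk has been ruled out.

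**Tolerability.** The earlier study reported no stops for discomfort, and at zero stops there is nothing to dilute. With an assumed 3 stops in an arm of 78 with 62 users, the figure is 3/78 = 3.8% if non-users are in the denominator and 3/62 = 4.8% if they are not.

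**Between-arm test, balanced non-use.** Two-sided Fisher p-values for assumed counts of affected participants:

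| Affected, active v sham | 78 per arm | 70 | 62 | 58 |
|---|---|---|---|---|
| 8 v 3 | 0.210 | 0.208 | 0.205 | 0.204 |
| 12 v 4 | 0.062 | 0.060 | 0.058 | 0.057 |

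The test barely changes. The absolute difference does change: 12 v 4 is 8/58 = 13.8 points on 58 per arm and 8/78 = 10.3 points on 78.

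**The case against.** The strongest reply is that dilution is not proven. Under the non-missing denominator in SAP 7.1 and the ban on imputation in SAP 6.2, a never-user with no AE observation period could fairly be treated as missing, and the percentage would then be correct. That stands as a possible reading. It is not the stated one, though, because the plan names all randomised participants as the safety set and does not say how non-users enter it.

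The top of the range is an upper bound, and this also stands. The 25% allowance covers everyone not evaluable, including users without a 2-hour score. In the earlier study 44/172 = 25.6% were lost to mITT against 20.3% lost to its safety population, so about 5 points may have been treated people. At 20.3% the gap is 1.0, 2.0, 4.1 or 6.1 points for rates among users of 5%, 10%, 20% or 30%.

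The rate may also be recoverable: SAP 9 tabulates participants with AEs and SAP 7.7 summarises exposure. That holds only if the exposure table counts users, and a primary safety figure should not need reconstruction by the reader.

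Unequal non-use between arms could distort the comparison, but nothing in the documents suggests it. Assignment sits in a sealed cartridge matched for size and weight, so balance is the reasonable expectation.

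Finally, the amendment summary records that a safety population was removed, so the choice looks deliberate. That does not make an all-randomised denominator suitable for a device-related incidence.

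**Conclusion.** The concern holds. The stated safety set includes people who cannot have the event being counted, no treated-only safety set exists, and the handling of non-users is unstated. If non-users are scored as having no AE, the printed incidence falls short of the rate among users by a relative amount equal to the never-use share: about a fifth if 137 of 172 in the earlier study reflects device use, and a quarter at the extreme. These sizes rest on assumed never-use and AE rates.

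The consequence is limited to absolute incidences, risk differences and confidence bounds. AE counts and listings are unaffected, Fisher's test changes little under balanced non-use, and no decision rule depends on the figure. It should be fixed, but it does not threaten the trial's main efficacy conclusion.

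**What to change.** In Protocol 11.3 and SAP 6.1, define a Safety Set: all randomised participants who started at least one device session, taken from the device-log start time, or from the app report where there is no log. Then:

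- Use it as the denominator for all AE and tolerability percentages.
- State whether arms are grouped as randomised or by treatment received.
- Remove the safety label from ITT in SAP 7.2. In SAP 7.4, 7.6 and 7.7, use the new set where users are meant and name ITT where all randomised are meant.
- Report the number of non-users by arm in the disposition table.
- Cover replacement supplies. Protocol 7.3 says of participants with an unresolved technical problem that "they may be shipped a replacement tubeset and desiccant cartridge to treat their next attack". If this produces more than one logged start, include the participant once and count AEs from the first start.

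The cost is wording in the protocol, SAP and table shells. Protocol 10.1 already has session start and stop times extracted from the returned device and entered in the EDC, so no new data are needed. The downside for the sponsor is that the reported percentages may be slightly less favourable.

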6.2. Missing Data

Missing values will not be imputed.

7. SUMMARY OF STUDY DATA

7.1. Data Display

Tables will have columns corresponding to or be stratified by the treatment groups where appropriate:

- Group I (Active Treatment)
- Group II (Sham Treatment))

In general, all data will be listed by treatment group, participant and visit/time point where appropriate. The total number of participants under the stated population (N) will be displayed in the header of summary tables.

Data will be summarized using descriptive statistics for continuous variables. Unless otherwise specified, descriptive statistics will include number of participants, mean, standard deviation, minimum, median, maximum and interquartile range. The statistic "Missing" will also be presented as the number of missing entries/participants, if any at that visit/timepoint, and presented as a summary statistic only when non-zero. The minimum and maximum statistics will be presented to the same number of decimal places as the original data. The mean and median will be presented to one more decimal place than the original data, whereas the standard deviation will be presented to two more decimal places than the original data.

In summary tables of categorical variables, counts and percentages will be used. The count [n] indicates the actual number of participants with a particular value of a variable or event, which should always be less than or equal to the total number of participants with non-missing value of the variable or event [M]. Percentage will be obtained by: $\% = (n/M)*100$. Unless otherwise stated, all percentages will be expressed to one decimal place. Both lower and upper limits will carry the same number of decimal places as the original value for 95% confidence intervals.

P-values will be displayed with 4 decimals, e.g., p=0.0001 and p-values below 0.0001 will be displayed as p<0.0001.

In by-visit summary tables only scheduled visits/timepoints will be summarized. In listings, all visits and timepoints with any data collected will be included.

The change from baseline values will be derived for each participant as the post-baseline evaluation minus the baseline evaluation.

All dates will be displayed in ISO 8601 date format (YYYY-MM-DD).

Table 1. Efficacy Endpoint Variables

Variable	Role	Data Source	Analysis Plan
2hr Pain Freedom	Primary Efficacy Endpoint	Baseline Migraine Symptom Questionnaire 2-hour Post Treatment Migraine Symptom Questionnaire	n% Achieved if Head Pain changes from Severe, Moderate, or Mild at baseline to None at 2hrs post-treatment.
2hr MBS Freedom	Secondary Efficacy Endpoint	Baseline Migraine Symptom Questionnaire 2-hour Post Treatment Migraine Symptom Questionnaire	n% Achieved if MBS changes from Severe, Moderate, or Mild at baseline to None at 2hrs post-treatment.
2-24hr Sustained Pain Freedom	Secondary Efficacy Endpoint	Episodic Rescue Medication Questionnaire Baseline Migraine Symptom Questionnaire 2-hour Post Treatment Migraine Symptom Questionnaire 24-hour Post Treatment Migraine Symptom Questionnaire	n% Achieved if Pain Freedom is sustained from 2 hours post-treatment until 24 hours with no administration of rescue medication and with no recurrence of a mild/moderate/severe headache.
2hr Pain Relief	Secondary Efficacy Endpoint	Baseline Migraine Symptom Questionnaire 2-hour Post Treatment Migraine Symptom Questionnaire	n% Achieved if Head Pain changes from Severe or Moderate at baseline to Mild or None at 2 hours post-treatment, OR if Head Pain changes from Mild at baseline to None at 2 hours post-treatment.
Global Impression of Acute Treatment Effect	Secondary Efficacy Endpoint	24-Hour Post Treatment User Experience Questionnaire	Patient Global Impression of Change measure
Rescue Medication use 0-2hrs Post Treatment	Exploratory Endpoint	Episodic Rescue Medication Questionnaire	

		2-hour Post Treatment Migraine Symptom Questionnaire	
0hr Pain Freedom	Exploratory Endpoint	Baseline Migraine Symptom Questionnaire Immediate Post Treatment Migraine Symptom Questionnaire	n% Achieved if Head Pain changes from Severe, Moderate, or Mild at baseline to None immediately post-treatment.
0hr Pain Relief	Exploratory Endpoint	Baseline Migraine Symptom Questionnaire Immediate Post Treatment Migraine Symptom Questionnaire	n% Achieved if Head Pain changes from Severe or Moderate at baseline to Mild or None immediately post-treatment, OR if Head Pain changes from Mild at baseline to None immediately post-treatment.
2-48hr Sustained Pain Freedom	Exploratory Endpoint	Episodic Rescue Medication Questionnaire Baseline Migraine Symptom Questionnaire 2-hour Post Treatment Migraine Symptom Questionnaire 48-hour Post Treatment Migraine Symptom Questionnaire	n%, Chi-Square Achieved if Pain Freedom is sustained from 2 hours post-treatment until 48 hours post-treatment, with no administration of either rescue medication and with no recurrence of a mild/moderate/severe headache.
0hr MBS Relief	Exploratory Endpoint	Baseline Migraine Symptom Questionnaire Immediate Post Treatment Migraine Symptom Questionnaire	n% Achieved if MBS changes from Severe or Moderate at baseline to Mild or None at 2 hours post-treatment, OR if MBS changes from Mild

			at baseline to None at 2 hours post-treatment.
2hr MBS Relief	Exploratory Endpoint	Baseline Migraine Symptom Questionnaire 2-hour Post Treatment Migraine Symptom Questionnaire	n% Achieved if MBS changes from Severe or Moderate at baseline to Mild or None immediately post-treatment, OR if MBS changes from Mild at baseline to None immediately post-treatment.
0hr MBS Freedom	Exploratory Endpoint	Baseline Migraine Symptom Questionnaire Immediate Post Treatment Migraine Symptom Questionnaire	n% Achieved if MBS changes from Severe, Moderate, or Mild at baseline to None immediately post-treatment.
0hr Nausea Freedom	Exploratory Endpoint	Baseline Migraine Symptom Questionnaire Immediate Post Treatment Migraine Symptom Questionnaire	n% Achieved if Nausea changes from Severe, Moderate, or Mild at baseline to None immediately post-treatment.
2hr Nausea Freedom	Exploratory Endpoint	Baseline Migraine Symptom Questionnaire 2-hour Post Treatment Migraine Symptom Questionnaire	n% Achieved if Nausea changes from Severe, Moderate, or Mild at baseline to None at 2hrs post-treatment.
0hr Photophobia Freedom	Exploratory Endpoint	Baseline Migraine Symptom Questionnaire	n% Achieved if Photophobia changes from Severe, Moderate, or Mild at baseline to None

		Immediate Post Treatment Migraine Symptom Questionnaire	immediately post-treatment.
2hr Photophobia Freedom	Exploratory Endpoint	Baseline Migraine Symptom Questionnaire 2-hour Post Treatment Migraine Symptom Questionnaire	n% Achieved if Photophobia changes from Severe, Moderate, or Mild at baseline to None at 2hrs post-treatment.
0hr Phonophobia Freedom	Exploratory Endpoint	Baseline Migraine Symptom Questionnaire Immediate Post Treatment Migraine Symptom Questionnaire	n% Achieved if Phonophobia changes from Severe, Moderate, or Mild at baseline to None immediately post-treatment.
2hr Phonophobia Freedom	Exploratory Endpoint	Baseline Migraine Symptom Questionnaire 2-hour Post Treatment Migraine Symptom Questionnaire	n% Achieved if Phonophobia changes from Severe, Moderate, or Mild at baseline to None at 2hrs post-treatment.

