5. SAMPLE SIZE CALCULATION

The sample size for this study was calculated to test the null hypothesis with a two-tailed Fisher's exact test.

The sample size is calculated to test the null hypothesis with 80% power at a 5% level of significance using PASS 2024 software, version 24.0.2.

If we assume that 41% of the participants in the active treatment arm will have pain freedom at 2 hours post treatment versus 16% in the sham arm, then 116 evaluable participants are required (58 per group). Allowing for a 25% dropout rate, a total of 156 (78 active versus 78 sham) participants should be enrolled in the study.

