8. EFFICACY ANALYSIS

The Pearson Chi-squared test will be used to compare randomized arms with regards to primary and secondary endpoints. Logistic regression modeling will estimate odds ratios and 95% confidence intervals for pain relief/freedom endpoints to compare the two groups. The absolute difference in rates of freedom from pain will be estimated with 95% confidence intervals. Binomial exact 95% confidence intervals will be constructed for the incidence of primary and secondary endpoints within each group.

All statistical analyses will be performed using Stata software (version 19, StataCorp LLC, College Station, Texas).

Deviations from the planned analysis will be described, with proper justification, in the clinical study report.

Type I Error: The overall significance level for this study is 5% using two-tailed tests

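### Sustained pain freedom 2-24 h has no rule for a missing 24-hour score; on the SAP's general rules, undetermined 2-hour responders leave the denominator while 2-hour failures stay in

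*SAP*

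**What the plan says.** SAP 3.2.2 lists SPF 2-24 h second among four secondary endpoints. SAP 8.2 tests these in a fixed sequence at 0.05 after the primary, each by a chi-squared test on counts and percentages. A failure at SPF ends formal testing of pain relief and of the global impression of change.

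- **Endpoint.** SAP 7.1, Table 1: "Achieved if Pain Freedom is sustained from 2 hours post-treatment until 24 hours with no administration of rescue medication and with no recurrence" of headache. The listed sources are the rescue medication questionnaire and the baseline, 2-hour and 24-hour symptom questionnaires.
- **Main set.** SAP 6.1.2 defines mITT as "All participants who used the study intervention and completed a baseline and 2-hour post-dose pain assessment". No 24-hour score is needed.
- **Missing data.** SAP 6.2: "Missing values will not be imputed".
- **Denominator.** SAP 7.1 computes percentages as n/M, where M is the "total number of participants with non-missing value of the variable or event [M".

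The only rule that treats a missing score as failure (SAP 8.1 and protocol 11.6.1) covers the 2-hour score, for the primary endpoint, in the ITT sensitivity analysis. Repeating the secondary analyses on ITT and PP (SAP 6.1) adds no rule for a missing 24-hour score.

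**The concern.** A participant who is not pain-free at 2 hours has failed SPF by definition, whatever the 24-hour form would have shown. A 2-hour responder with recorded rescue before 24 hours has failed as well. Only a 2-hour responder with neither a 24-hour score nor recorded rescue is undetermined. If SAP 6.2 and 7.1 decide the matter, that person drops out of M and the known failures do not. Being counted then depends on 2-hour response, which is itself a component of the endpoint.

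The primary endpoint is protected in the main analysis, because mITT guarantees its score. SPF is not. SPF is also tested only after 2-hour pain freedom has differed between arms, so the arms are expected to have unequal numbers of people who could be dropped. At stake are the durability result and access to the last two tests in the sequence.

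**Working it through.** **The plan's own figure.** Inputs from SAP 5 and 8: two-sided 5%, 80% power, 41% vs 16%, Fisher's exact test. Exact power is 0.799, 0.808 and 0.817 at 56, 57 and 58 per arm, and the continuity-corrected formula gives 58. Then 58/0.75 = 77.3, rounded up to 78 per arm, or 156 in total. The stated sample size reproduces and is not in question. It supplies the arm size and the 2-hour rates used below.

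**Inputs for SPF**
- 2-hour pain freedom p = 0.41 active, 0.16 sham (SAP 5).
- Share of responders sustained s = 0.88. Protocol 3.2 reports this share still pain-free at 24 hours in the 10 LPM group of the earlier dosing study. It is not exactly SPF, since one of those participants had used rescue. Applying it to both arms is an assumption.
- Share of responders without a 24-hour score, m: not in the documents. Assumed 10% to 30%.

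**Three readings**
1. Drop only undetermined responders: ps(1−m)/(1−pm).
2. Drop everyone without a 24-hour score, with mn the missing share among non-responders: ps(1−m)/[p(1−m)+(1−p)(1−mn)].
3. Count missing as not achieved, full mITT denominator: ps(1−m).

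**Missing at random among responders.** The truth is 0.41×0.88 = 36.1% vs 0.16×0.88 = 14.1%, a difference of 22.0 points.

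| m | Reading 1 | Difference | Reading 3 | Difference |
|---|---|---|---|---|
| 10% | 33.9% vs 12.9% | 21.0 | 32.5% vs 12.7% | 19.8 |
| 20% | 31.4% vs 11.6% | 19.8 | 28.9% vs 11.3% | 17.6 |
| 30% | 28.8% vs 10.4% | 18.4 | 25.3% vs 9.9% | 15.4 |

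Under reading 2 with mn = m, the formula reduces to ps, so the true 22.0 points are recovered. It departs from the truth only if missingness differs by response.

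**Missing among relapsers, reading 1.** If a share q of relapsers lack the score, the expected rate is ps/[1−p(1−s)q].
- s = 0.70, q = 1: the truth is 28.7% vs 11.2% (17.5 points). Reading 1 gives 0.287/(1−0.123) = 32.7% vs 0.112/(1−0.048) = 11.8%, or 21.0 points.
- True SPF 14% in both arms, q = 0.5: relapsers are 0.41−0.14 = 0.27 and 0.16−0.14 = 0.02. Reading 1 gives 0.14/(1−0.135) = 16.2% vs 0.14/(1−0.01) = 14.1%, a difference where none exists. Reading 3 gives 14% vs 14%, because no sustained responder is missing.

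**Effect on the gate.** Constructed counts with 58 per arm and 24 vs 9 two-hour responders, Pearson chi-squared without correction:
- 15 vs 7 sustained; 4 active and 1 sham responder undetermined. Reading 1: 15/54 vs 7/57, p = 0.041. Reading 3: 15/58 vs 7/58, p = 0.058.
- 14 vs 6 sustained; 0 active and 2 sham undetermined. Reading 1: 14/58 vs 6/56, p = 0.060. Reading 3: 14/58 vs 6/58, p = 0.049.

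**The case against.** The strongest reply is that this is an ambiguity and not a stated exclusion. The n/M rule sits under data display, and SAP 8.2 names a test without a denominator. Table 1 says when SPF is achieved, so a programmer could fairly code a participant without 24-hour evidence as not achieved, which is reading 3. This stands. A reader might infer that the plan definitely drops these responders. The documents do not go that far: it follows from the only general missing-data and denominator rules given, but the text does not rule out the other two readings.

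A reader might also infer that every complete-case approach makes inclusion depend on outcome, or that the bias favours the device. Neither is supported. Dropping everyone without a 24-hour score discards known failures, but it biases the result only if missingness differs by response, and the documents give no evidence on that. The direction under reading 1 depends on who is missing.

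The effect may also be small. With random loss of 10% it is about 1 point, towards no difference. The rescue form is open throughout follow-up (protocol 5), which lets some relapsers be classified without a 24-hour score, and compliance is reviewed daily in business hours (protocol 12.4). The gate examples are constructed near p = 0.05.

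Finally, under random missingness, counting missing as failure lies further from the truth than reading 1. This stands too, so the case for it cannot rest on accuracy in that scenario.

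**Conclusion.** The gap is real. For a gated endpoint, neither document says how SPF is classified when the 24-hour score is absent, and the SAP's general rules point to a denominator that depends on 2-hour response. The size cannot be known in advance. Under the stated assumptions it is 1.0 point at 10% random missingness and 2.2 points at 20%, both towards no difference. If all relapsers are missing and 70% of responders are sustained, it is 3.5 points upward. The choice matters for the conclusion only when the result is near 0.05, and then in either direction. The primary endpoint in mITT and the sample size are unaffected.

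The reason to prefer the full mITT denominator is protection against a false positive. SPF is tested only once 2-hour response has differed. If true SPF is equal, counting missing as not achieved keeps the arms equal as long as missingness among sustained responders is the same in both. Reading 1 does not, when relapsers go missing.

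**What to change.** Before unblinding, add to the SAP a value of SPF 2-24 h for every mITT participant:

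- Not pain-free at 2 hours, any recorded rescue in the window, or any recorded recurrence: not achieved, whether or not a 24-hour score exists.
- Pain-free at 2 hours with no 24-hour score: not achieved in the gated test.
- The denominator for the percentage and for the chi-squared test is the full mITT N.
- A complete-case analysis is run as sensitivity, stating exactly whom it drops.
- The same rules apply to SPF 2-48 h with the 48-hour score.

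The cost is a few SAP sentences and no new data. The downside is statistical: this is a conservative convention and not an unbiased estimate. Under random missingness it shrinks both rates and their difference in proportion to the missing share, from 22.0 to 19.8 points at 10% and to 17.6 at 20%. The report should say so and give the number of undetermined responders by arm.
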